7.2 Baseline Descriptive Statistics

The initial 8-week screening period for each randomized participant is considered to be the baseline evaluation period. Baseline statistical analyses will consist of descriptive statistics (means and standard deviations, medians and first and third quartiles, and minimums and maximums) for continuous baseline measures such as current age, age at first asthma diagnosis, baseline pulmonary function parameters (including methacholine hyperresponsiveness), and asthma symptom severity. Categorical and binary variables such as gender, prior medication history, atopic status, and asthma-relevant genotypes will be summarized as number and percentage for each category. Poisson-type outcomes, such as exacerbations, will be summarized as event rates.

Predictive biomarkers will be assessed at baseline and summarized according to the distributions of values as well as the number and percentage of participants in and out of the target subgroup for each intervention. Predictive biomarkers are re-assessed throughout the study, but the determination of participant biomarker profiles for purposes of treatment assignments are based on the baseline values of predictive biomarkers and not modified during the study.

7.3 Unblinding for Interim and Final Analyses of Each Intervention

Both interim and final analyses for each intervention are conducted independently of other interventions, consistent with the master protocol design. Statistical analyses for Intervention A are based on participants randomized to Intervention A during the trial. The treatment periods in which participants were randomized to A plus matched placebo periods contribute to the analysis. For participants without a matched placebo, all placebo periods will be included in the analysis. For analyses based on the mITT and per protocol populations, the treatment periods included in the analyses are limited to those satisfying the respective mITT and per protocol criteria stated above. Other treatment periods from the participant might be used in the analysis to estimate the within-participant correlation in the crossover if the primary model does not converge.

The target sample size for the interim analysis of Intervention A, with objective to test for futility, is 34 biomarker positive participants and 17 biomarker negative participants.

Once an intervention achieves the target sample size for an interim analysis, an appropriate data cut-off is determined for the interim analysis (sufficient to allow completion of data acquisition for the treatment periods contributing to the analysis), analysis files are generated, and analyses conducted by the independent unblinded project statistician for submission to the DSMB.

Upon achievement of the final target sample size for an intervention (111 participants), randomization to that intervention stops. Because interventions may stop at different times in the study, and placebo period data are shared across interventions, care will be taken to observe firewalls that protect confidentiality of data and analysis results for one intervention while other interventions continue to accrue participants. If, for example, data for Intervention A are reported publicly, while the study continues (e.g., A was stopped early for futility), then information about placebo periods included in the

report for A will be limited to comparative group analysis results only. No rare events or within-group event rates that could potentially unblind treatments in the ongoing trial or motivate conjecture about the results of the ongoing interventions will be reported.

Study close-out procedures will not be implemented until all interventions are completed.

7.4 Analysis of Primary Efficacy Endpoints

7.4.1 Statistical Model

The final analysis to assess the efficacy of an intervention will be performed when accrual and follow-up for that intervention are complete and will include biomarker positive and biomarker negative participants randomized to the intervention unless the biomarker negative subgroup is dropped after the interim futility analysis, i.e., cavosonstat. In this case, the primary analysis will include only biomarker positive participants assigned to that intervention. Data from the treatment period in which a participant was randomized to the intervention plus the matched placebo period associated with that participant are included in the final analysis of the intervention. If there is no matched placebo, all placebo periods obtained on that participant are included.

Treatment effects with respect to each of the two primary endpoints (FEV₁ and ACQ-6) will be estimated using a mixed model for repeated measurements (MMRM) that appropriately takes into account the within-participant correlations between periods. The MMRM will include treatment (test vs placebo), time (visit nested within period), subgroup levels and baseline values (FEV₁ and ACQ-6), measured before the first randomization, as fixed effects. The model will also include two-way interactions (fixed effects) between treatment and time and baseline and time. Subgroup-specific treatment effects will be estimated by including subgroup by treatment interaction. Unstructured variance-covariance matrix will be used to model covariances within each treatment period. If the model does not converge with an unstructured variance-covariance matrix, the Toeplitz variance-covariance matrix will be used. The model will include a subject-level random intercept to model between-period correlation. If the model fails to converge, other variance-covariance structures will be evaluated until model convergence is achieved. If the variance-covariance matrix in MMRM cannot be estimated well, we will include more data on the participants in the analysis population for that intervention.

For a given intervention and outcome let T_k^* be the test statistic for the treatment effect in biomarker positive participants and T_k^{All} be the test statistic in all participants computed using stage k , $k = 1, 2$, data. The tests are from the corresponding MMRM (subscripts indicating intervention and outcome are omitted here). In the final analysis, the treatment effect of a given intervention with respect to that outcome is performed using the inverse normal combination approach by computing the p-value: $p = 1 - \Phi(\sqrt{0.45} \Phi^{-1}(1 - p_1) + \sqrt{0.55} \Phi^{-1}(1 - p_2))$. Here p_1 and p_2 are the stage 1 and stage 2 p-values. The first stage p-value, p_1 , is computed based on the test statistic $\max(T_1^*, T_1^{All})$ using the skew normal distribution with parameters $(0, 1, .32)^6$ as a reference distribution. If the biomarker negative subgroup is not dropped at the interim analysis, the second stage p-value is computed similarly to the stage 1 p-value. If the biomarker negative subgroup is dropped at the interim analysis, the second stage p-value, p_2 , is computed based on the test statistic T_2^* using the standard normal distribution as a reference distribution. The weights $\sqrt{0.45}$ and $\sqrt{0.55}$ in the inverse normal formula correspond to a futility analysis performed at the 0.45 information fraction. If futility is performed at an information fraction xt , the weights \sqrt{x} and $\sqrt{1-x}$ will be used. For interventions without an interim analysis, the final analysis for a given outcome is performed as follows. Five possible cutoffs b_1, b_2, b_3, b_4, b_5 are identified for the primary continuous biomarker that defines the biomarker positive subgroup for that intervention. The five potential subgroups are defined as participants with the biomarker values $\geq b_i$ if the treatment effect is assumed to be increasing with the biomarker values, and $\leq b_i$ otherwise. The test statistic $\max(T^1, T^2, T^3, T^4, T^5, T^{All})$ is compared with 2.163 for a 0.05 one-sided level and with 2.452 for a 0.025 one-sided

level. These critical values were computed based on the joint distribution of the six test statistics under the null hypothesis and assuming that the cutoffs represent the quantiles of the biomarker distribution.⁷

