## 9 STATISTICAL CONSIDERATIONS

### 9.1 STATISTICAL HYPOTHESES

Two primary endpoints are specified to assess treatment efficacy (study objective #1):

- 1) **FEV1 percent predicted**, assessed prior to bronchodilator administration
- 2) **Asthma symptom control**, assessed via the Juniper Asthma Control Questionnaire (ACQ-6)

FEV1 percent predicted and ACQ-6 score will be measured at the start and the end of each treatment period. Efficacy analyses will compare the end-of-period outcome values between test treatment and placebo.

For the first primary study objective (overall assessment of efficacy), the following hypotheses will be tested:

1. Test treatment T does not improve FEV1 percent predicted compared to placebo (the null hypothesis) versus T is different from placebo.
2. Test treatment T does not improve asthma symptom control assessed via ACQ-6 compared to placebo (the null hypothesis) versus T is different from placebo.

The second primary objective involves estimation of the optimal subgroup for targeting participants for each intervention. No formal statistical hypotheses will be tested for this objective.

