### 9.2 SAMPLE SIZE DETERMINATION

An intervention is considered efficacious if significant benefit is shown for either of the two primary endpoints (FEV1% predicted, and ACQ-6). Because there are multiple chances for a test treatment to

demonstrate efficacy, multiplicity adjustments are required. We will use the Hochberg method to adjust for multiplicity.

A sample size of 111 participants is required to achieve 80% power to detect a treatment effect with respect to at least one of the two primary endpoints equal to 0.3 times the standard deviation (SD) of that endpoint, taking into account the possibility to stop for futility. The Type I error probability will be controlled under the global null hypothesis (no effect on either endpoint) at  $\alpha \leq 0.10$ . Power was estimated under the assumption of a within-participant, between-period correlation of responses on consecutive placebo and test treatment,  $\tau$ , of 0.70 and a treatment period discontinuation rate of 0.10. The required sample size for interventions with treatment period drop-out rates significantly different from 0.10, assessed based on pooled placebo and active treatment data, may be adjusted during the trial, prior to any unblinding. If futility analysis is not feasible for an intervention due to difficulty in participant accrual, 93 participants (2:1 ratio of biomarker positive to negative participants) are required to provide the same power described above.

Examples of treatment effects yielding a 0.3 standardized effect size include: a difference of 4.3 percent predicted FEV1 between intervention and placebo with a SD of 14.5 percent predicted; and a difference of 0.18 in average ACQ-6 symptom scores between the intervention and placebo with a SD of 0.6.

Given the experimental nature of the trial, the Type I error rate will be controlled at the two-sided 0.1 level. Our analysis method ensures a strong control of the Type I error rate at this level. Taking into account our stopping rule for futility, the Type I error rate is equal to about 0.05, two-sided, for  $\tau = 0.70$ .

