4.3 Assignment of Test Treatment versus Placebo and Masking

Each intervention has its own placebo that matches the test treatment in mode of administration, color, size, and/or taste.

In the first two periods, each participant will receive a test treatment and its matching placebo, with the order being randomly determined (crossover sequence allocation). During subsequent treatment periods (periods 3-6), the placebo assignment probability is initially set to 0.17 but monitored throughout the study and adjusted as needed to yield, on average, approximately 25% of all participants receiving a second placebo. Once a participant receives a 2nd placebo, their probability of receiving placebo in subsequent periods is set to 0 (with some exceptions – see below). This strategy results in

participants enrolled earlier and therefore eligible for more treatment periods having a higher chance of receiving a second placebo than participants enrolled later in the trial.

If a participant discontinues treatment during periods 1 or 2 such that no post-baseline assessments of the FEV₁ percent predicted and ACQ-6 are available, the probability of their receiving placebo in periods 3 and 4 might be adjusted to ensure the participant will have efficacy evaluable data from at least one placebo period during the study. In period 3, the probability of receiving placebo = 0.5, and in period 4, the probability = 0 if placebo is received in period 3, and = 1 otherwise. The participant is also eligible to receive another placebo in periods 5-6 with the same probability as any other participant. A participant may therefore be randomly assigned placebo at most three times during the study and will contribute efficacy data to the statistical analysis from at most two placebo periods.

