An intervention is considered efficacious if significant benefit is shown for either of the two primary endpoints (FEV₁, or asthma symptom control score). Because there are multiple chances for an intervention to demonstrate efficacy, multiplicity adjustments are required. We will use the Hochberg method to adjust for multiplicity. According to the Hochberg method, the treatment is declared effective if the treatment-placebo comparison is significant at level α for both outcomes or it is significant at $\alpha/2$ for at least one of the outcomes.

A sample size of 111 participants for each intervention is required to achieve at least 80% power to detect a treatment effect with respect to at least one of the two primary endpoints equal to 0.3 times the standard deviation (SD) of that outcome, taking into account the possibility of stopping for futility with a non-binding stopping rule. If participant accrual in the target subgroup of one or more interventions is such that an interim futility analysis is not possible or practical (e.g., the study will conclude before the recommendations of the interim futility analysis can be implemented), the interim analysis will not be performed. In this case, 93 participants (2:1 ratio of biomarker positive to negative participants) are required to provide similar power for the final analysis.

All participants randomized to an active intervention or matching placebo will be included in the final efficacy analysis, but only participants who do not withdraw from the study prior to the start of period 2 are counted towards the required total sample size in estimating power. We also assume that about 10% of participants will discontinue an active treatment period soon after randomization in the power calculations. Attrition is monitored throughout the study, and the required sample size may be adjusted, if the treatment discontinuation rate is different from 10% or discontinuations occur later in the treatment period. This adjustment, if needed, will take place prior to any unmasking of treatment assignments, that is, prior to the interim futility analysis or, if the futility analysis is not feasible for an intervention, prior to the final analysis.

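### SAP 7.4.1 fits a separate treatment effect in every period but never says how these are combined, and an equal-weight average often cannot be estimated

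*SAP*

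**What the plan says.** SAP 7.4.1 lists the fixed effects: "The MMRM will include treatment (test vs placebo), time (visit nested within period), subgroup levels and baseline values". It then adds: "The model will also include two-way interactions (fixed effects) between treatment and time and baseline and time". SAP 3.5.1 has on-treatment visits X.2 to X.5 in periods 1 to 6, so time has up to 6 x 4 = 24 levels.

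The visit of interest is settled. SAP 3.5.1 names X.5 as the endpoint visit, and Protocol 9.1 says: "Efficacy analyses will compare the end-of-period outcome values between test treatment and placebo". SAP Table 2 asks for one mean difference per endpoint, and the tests in SAP 7.4.1 use one statistic in biomarker positives (T*) and one in all participants (T_All), by stage. Neither document gives weights over periods.

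Three rules decide how much placebo data each period holds:
- SAP 7.4.1: a participant with a matched placebo contributes that placebo only. Without a match, all of the participant's placebo periods enter.
- SAP 4.3, on periods 3-6: "the placebo assignment probability is initially set to 0.17".
- SAP 4.1: about 25% of participants are meant to receive a second placebo.

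The fallbacks in SAP 7.4.1 deal with convergence and the covariance matrix. They do not cover a fixed effect that cannot be estimated.

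**The concern.** Periods 1 and 2 form a balanced crossover, so each holds ample test and placebo data. From period 3 on, most records in an intervention's analysis set are active, and the placebo comparison for those participants mostly comes from their own period 1 or 2. A model with one treatment effect uses that within-participant comparison. A model with an effect for each period does not pool it automatically. The effect in period 5, say, needs placebo records in period 5. If there are none, that effect is not estimable, and neither is any average that gives it positive weight.

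Every primary p-value comes from this model, and SAP 7.5 reuses the MMRM for FVC, post-bronchodilator FEV1, symptom-free days and asthma-free days. If the contrast is left open, the precision of the primary test, and whether it can be computed at all, is not fixed by the plan.

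**Working it through.** **1. The plan's own figures.** Inputs from SAP Section 5 and Protocol 9.2: effect 0.3 SD, between-period correlation 0.70, 10% loss of treatment periods, Hochberg over two endpoints, two-sided 0.10. For the design without a futility analysis the SAP states: "93 participants (2:1 ratio of biomarker positive to negative participants) are required to provide similar power for the final analysis".

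- SE of the paired contrast = sqrt(2(1 - 0.7)/(0.9n)). For n = 93 this is sqrt(0.6/83.7) = 0.0847 SD; for n = 111 it is sqrt(0.6/99.9) = 0.0775 SD.
- Effect in biomarker positives only: n = 62, SE = sqrt(0.6/55.8) = 0.1037, so T* has mean 0.3/0.1037 = 2.89. T_All has mean 0.2/0.0847 = 2.36. Their correlation is sqrt(2/3).
- Critical values for the larger of the two: 2.147 (one-sided 0.025) and 1.840 (one-sided 0.05). The second endpoint is taken as null and independent.
- Power is 0.798 at n = 92 and 0.802 at n = 93. The stated 93 is reproduced.
- Futility under the null: each endpoint has both statistics below 1.29 with probability 0.860, and 0.860 squared is 0.740. The stated 0.74 is reproduced.

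This uses the two-statistic maximum. SAP 7.4.1 tests interventions without an interim analysis on a six-statistic maximum, so the match serves here only to link SE to power.

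**2. How full the cells are.** The platform was simulated with 395 participants, up to six periods, 2% withdrawal per 4 weeks, placebo probability 0.17 in periods 3-6, at most one second placebo, 10% period loss, a cap of 111 or 93 per intervention, and the placebo rule of SAP 7.4.1. Accrual was set to give the roughly 1000 periods forecast in SAP 1.3. Mean records per intervention with the cap at 111:

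| Period | 1 | 2 | 3 | 4 | 5 | 6 |
|---|---|---|---|---|---|---|
| Active | 35 | 27 | 21 | 8.5 | 3.4 | 1.0 |
| Placebo | 44 | 48 | 2.5 | 2.2 | 1.2 | 0.4 |

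Periods 3-6 hold 33.9 of 95.9 active records (35%) but 6.3 of 98.3 placebo records (6%).

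**3. Consequence for the week-16 contrast.** Generalised least squares on the week-16 value used a random-intercept correlation of 0.7, period effects and baseline-by-period. The reference is the same model with one treatment effect. It was estimable in every data set, with SE about 0.095 SD (cap 111) and 0.103 SD (cap 93). Adding treatment-by-period gave:

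| Contrast over periods | Median SE ratio to common-effect model, where estimable |
|---|---|
| Equal weights, all periods | 2.3-2.6 |
| Weighted by active records | 1.3-1.4 |
| Weighted by all records | 1.06-1.10 |
| Precision weights | 1.00 |
| Periods 1 and 2 only, equal weights | 1.06-1.09 |

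The equal-weight contrast was non-estimable in 72-84% of sets. Where it was estimable, the ratio exceeded 2 in 75-82%. Fits by stage (51 participants, then the remaining 60) were non-estimable in 93-95%. In the few that were estimable, the median ratio was about 1.8-1.95.

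**4. Sensitivity of the equal-weight result.** At about 1130 periods: non-estimable 37-61%, ratio 2.0-2.2. At about 1400 periods: non-estimable 10-52%, ratio 1.5-1.7. A correlation of 0.4 or 0.85 changed little.

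**5. What a ratio means for power.** Multiplying the planned SEs in step 1 (n = 93, power 0.80): a ratio of 1.3 gives 0.58, 1.5 gives 0.47, 2.0 gives 0.30.

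**The case against.** The best defence is that this is loose drafting around a clear intention. Table 2 asks for one mean difference, SAP 7.4.1 speaks of the treatment effect in the singular, and the CompEx model in SAP 7.5 has treatment and period number with no interaction between them. SAP 7.4.3 treats averaging of period-1 and period-2 effects as a sensitivity analysis. The endpoint visit is fixed at X.5, so only the period weights are open. All of this stands. It shows what was probably meant, but the model sentence says something else and the fallbacks do not repair it.

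A reader might infer that the model itself makes the week-16 effect non-estimable or more than doubles its SE. The documents do not support that. It follows from equal weights, the usual least-squares-means default, which the SAP does not name. Other weights cost little or nothing, although record-based weights also fail when a positively weighted period has only one treatment.

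A reader might also measure the loss against the planned 0.077 SD. The common-effect model does not reach that figure in these data sets either (about 0.095-0.103 SD), so the fair comparison is between the two models on the same data. On that basis periods 1 and 2 alone keep about 84-89% of the information (1/1.09² to 1/1.06²), so later participants are not simply thrown away.

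Finally, a reader might infer that the contrast will be chosen after seeing results. SAP 6.1 requires programs to be specified before programming, and SAP 1.4 reserves SAP changes after unblinded review to blinded statisticians. Cell counts by period are not outcome data. No bias or error inflation follows from the text alone.

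**Conclusion.** The point holds as a gap in the primary analysis. The model as written has period-specific treatment effects, the test needs a single effect, and nothing links the two. It is more than a missing detail: at the SAP's own period forecast, the most usual contrast fails in most simulated data sets and in nearly all stage-wise fits, and permissible contrasts differ in SE by a factor of more than two on the same data.

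The size is conditional. It rests on an assumed shape of accrual, equal assignment among eligible interventions, an 8-week washout for all interventions, and a week-16 model in place of the full multi-visit MMRM. It shrinks with more accrual or other weights. No harm from the baseline-by-time interaction was shown.

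**What to change.** Amend the interaction sentence in SAP 7.4.1:
- Keep visit-within-period as a main effect.
- Replace treatment-by-time with treatment-by-visit, with visits X.2 to X.5 common to all periods.
- State that the primary contrast, used for T* and T_All at each stage, is the test-placebo difference at X.5 from this model.
- Examine treatment-by-period only as a supportive check.

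Changing baseline-by-time to baseline-by-visit is optional. If period-specific effects are truly wanted, the alternative is to pre-specify the period weights and a rule for periods with only one treatment.

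The cost is about one sentence, which SAP 1.4 allows the blinded team to change. The one statistical price is that the primary estimate assumes the same treatment effect in every period. That fits the single mean difference in Table 2 and the form of the CompEx model in SAP 7.5.

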4.2 Intervention Assignment

Each of the five interventions has a target (biomarker positive) subgroup defined based on a priori information available at the time the intervention enters the trial (Table 1). Each participant's status relative to the target subgroups is based on the biomarker profile determined at screening.

The target subgroups initially defined for each intervention have some degree of overlap, such that participants may be in the target subgroup for more than one intervention. In this sense, the interventions are competing with each other for targeted participants. The 1st-step randomization probabilities are applied to determine which intervention a participant is assigned among those interventions for which they are eligible. These probabilities are adjusted throughout the study to ensure the study objectives can be met. That is, accrued data on intervention eligibility and biomarker profiles (target subgroup membership) are monitored during the study, and randomization probabilities adjusted as needed to ensure a sufficient number of treatment periods (test and placebo) are available to support the planned interim (futility) and final (efficacy and precision medicine) analyses.

The initial randomization algorithm, implemented at study start, was guided by the following principles, given in priority order:

1. Interventions that have not yet reached the required sample size to test for futility are favored over interventions that have already enrolled enough subjects to conduct the futility analysis.
2. Interventions are randomly assigned to favor participants in the target subgroup of an intervention over participants outside that subgroup in 2:1 ratio, until the time of the interim analysis for futility.
3. Intervention assignment takes into consideration the distribution of three prognostic factors for asthma outcomes: (i) past-year exacerbations at the study's baseline (assessed during the initial screening period), (ii) blood eosinophils, and (iii) IL-6 plasma levels. The goal is to ensure that participants contributing to the efficacy analysis (interim and final) of each intervention resemble the severe asthma subpopulation with respect to these three factors. Initial targets for balancing were based on the factor distributions in the SARP population of severe asthma patients and are updated as PrecISE baseline data become available.

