The Type I error probability will be controlled under the global null hypothesis (no effect on either endpoint) at $\alpha \leq 0.10$ two-sided. Power was estimated under the assumption of a within-participant, between-period correlation of responses in consecutive placebo and test treatment periods of 0.70.

Examples of treatment effects yielding a 0.3 standardized effect size include: a difference of 4.3 percent predicted FEV₁ between intervention and placebo with a SD of 14.5 percent predicted; and a difference of 0.18 in average ACQ-6 symptom scores between the intervention and placebo with a SD of 0.6.

Our analysis method ensures strong control of the Type I error probability at $\alpha = 0.10$ two-sided for each intervention. This value was chosen to reflect the experimental nature of this phase 2 proof-of-concept study. Taking into account both our stopping rule for futility and the Hochberg method for controlling multiplicity due to multiple primary endpoints, the Type I error probability is expected to equal about 0.05. Interventions that demonstrate evidence of efficacy in PrecISE with respect to at least one of the two primary endpoints may be studied further in a more fully powered phase 3 trial to provide substantial evidence of efficacy, controlling the Type I error probability at the more usual level of 0.05. Information learned from PrecISE regarding the optimal target subgroup for the intervention should be useful in developing an enrichment strategy for such a study.

No adjustment for multiplicity with respect to the multiple interventions in the study is planned. Success is defined independently for each intervention, and interventions will not be compared to each other in the efficacy analyses.

We are planning to enroll 395 participants. Assuming a study withdrawal rate of 2% a month, we anticipate that each participant will contribute data to two active interventions on average. This will allow us to accumulate required number of active treatment periods to test efficacy in all five interventions.

6. Data Sources, Documentation, and Verification of Results

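### The fixed skew-normal shape of 0.32 in the primary test is exact only near 67% biomarker positives, and the SAP gives no rule for updating it if the stage 2 mix differs

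*SAP*

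**What the plan says.** For an intervention with an interim, SAP 7.4.1 takes the larger of T* (biomarker positives) and T_All (all participants) in stage 1 and obtains its p-value "using the skew normal distribution with parameters" (0, 1, 0.32). If biomarker negatives are kept, "the second stage p-value is computed similarly to the stage 1 p-value". If they are dropped, stage 2 rests on T* alone, "using the standard normal distribution as a reference distribution". The two p-values are combined with weights that "correspond to a futility analysis performed at the 0.45 information fraction". A sentence beginning "If futility is performed at an information fraction" lets those weights follow the fraction actually reached. No such rule is given for the shape.

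On the mix of participants:
- SAP 7.3: the interim target "is 34 biomarker positive participants and 17 biomarker negative participants". Randomization then stops at 111 in total, with no split by biomarker status.
- SAP 4.2: target participants are favoured "over participants outside that subgroup in 2:1 ratio, until the time of the interim analysis for futility", and assignment probabilities are re-tuned as needed to reach the required sample sizes.
- SAP 1.3: accrual to low-prevalence positive subgroups has been difficult.
- Protocol synopsis: at least 74 of the 111 should be targeted by the intervention.
- SAP 7.7.1: the sample size assumes 67% positives, and adjustments might be made if the parameters differ.

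On error control, SAP section 5 says: "Our analysis method ensures strong control of the Type I error probability at" 0.10 two-sided for each intervention. It also calls the futility rule non-binding.

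**The concern.** The null distribution of max(T*, T_All) depends on the correlation of the two statistics, which in turn depends on the share of information that comes from positives. A fixed shape builds one value of that share into the primary p-value. With fewer positives, T* and T_All are less correlated, their maximum tends to be larger, and the fixed reference gives p-values that are too small. With more positives it gives p-values that are too large.

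The SAP recognises that the information fraction may not come out as planned and adapts the weights. It does not do the same for the mix, although its explicit 2:1 statement ends at the interim. At stake is whether the strong-control statement is exact for interventions that keep their negatives after the interim, and whether a choice about the primary p-value would be left open until after unblinding.

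**Working it through.** **Inputs.** Shape 0.32 and weights from 0.45 and 0.55 (SAP 7.4.1); 34 positives and 17 negatives at the interim (SAP 7.3 and 7.7.1); futility cutoff 1.29, cutoff for dropping negatives 1.08, and stated null futility probability 0.74 (SAP 7.7.1); 111 participants, at least 74 targeted (protocol synopsis); 0.10 two-sided, that is 0.05 one-sided, with Hochberg over two endpoints (SAP section 5).

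**Formula.** The maximum of two standard normals with correlation r is skew normal (0, 1, λ) with λ = sqrt((1 − r)/(1 + r)). With equal outcome variance and equal information per participant in the two subgroups (assumption), r = sqrt(p), where p is the share of positives.

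**Reproducing the plan's figures.**
- p = 34/51 = 0.667 gives r = 0.8165 and λ = sqrt(0.1835/1.8165) = 0.318, which rounds to 0.32. Shapes that round to 0.32 correspond to p from 0.654 to 0.672.
- With shape 0.32, P(max < 1.29) = 0.8597. For two independent endpoints, 0.8597² = 0.739, against 0.74 in the SAP.

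So 0.32 is right for the planned mix, and it carries the 67% assumption.

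**Stage level at another mix.** With shape 0.32 the one-sided 0.05 critical value is 1.840. At p = 0.50, r = 0.7071 and λ = sqrt(0.2929/1.7071) = 0.414, so the true chance of exceeding 1.840 is 0.0539.

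**Whole procedure.** Simulation of 2 million null trials per row (Monte Carlo error about ±0.0003), with independent endpoints, stage 1 at 67% positives, Hochberg at 0.05 one-sided and shape 0.32 kept. SAP 7.7.1 does not say how the 1.08 cutoff combines the two endpoints. I assumed that negatives are dropped when both are below it, which happens in 0.860² = 0.74 of null trials. The last column, by numerical integration, keeps negatives in every trial and ignores the futility stop.

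| Stage 2 share positive | Exact shape | True stage size at nominal 0.05 | Family-wise error, futility stop ignored | Same, futility stop followed | Negatives always kept |
|---|---|---|---|---|---|
| 33% | 0.520 | 0.0574 | 0.053 | 0.041 | 0.057 |
| 50% | 0.414 | 0.0539 | 0.0515 | 0.040 | 0.053 |
| 66.7% | 0.318 | 0.0499 | 0.050 | 0.039 | 0.050 |
| 80% | 0.236 | 0.0460 | 0.048 to 0.049 | 0.037 | 0.046 |

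With the exact shape for each stage, the family-wise error with the futility stop ignored returns to about 0.050 in every row.

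**Which rows the plan allows.** If stage 1 is 34 of 51 and the minimum of 74 of 111 is kept, stage 2 has at least 74 − 34 = 40 positives among 111 − 51 = 60, or 67%. Only the 66.7% row and those above 67% are then reachable. The 50% and 33% rows require the minimum to be missed; the documents plan no such mix, so they illustrate a range.

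**The case against.** The case for leaving the text alone is substantial.

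- *The plan holds the mix near 67%.* Stage 1 is set at 34:17, the protocol sets a minimum on targeted participants, and re-tuning of the assignment serves the required sample sizes. This stands, and it means that adherence to plan leaves only the exact or conservative direction. But the requirement is a minimum and not a fixed ratio, the SAP's stopping target of 111 carries no split, and the SAP itself reports difficulty in accruing positives.
- *The shape is often not used.* It plays no part in stage 2 once negatives are dropped (SAP 7.4.1 names cavosonstat), nor where no interim is held, since those interventions use fixed critical values for six statistics. This stands and limits the scope.
- *The futility stop absorbs any inflation.* Numerically it does: about 0.041 at worst in the table. It cannot support strong control, because the SAP makes the rule non-binding.
- *The text already permits an update.* The word similarly in 7.4.1 could mean the same method with a new shape, and 7.7.1 allows adjustments. But the 7.7.1 sentence follows the sample-size statement, is optional, and gives no rule for the reference distribution.

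A reader might also infer two stronger points that the documents do not support. One is that both stages drift, which would give 0.055 at 50% and 0.060 at 33%; that requires stage 1 to miss the planned 34:17. The other is that the Table 1 prevalences of 33% to 64% are the expected mix. They are SARP population estimates, whereas assignment deliberately favours target participants.

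**Conclusion.** The point holds as a minor one. The fixed shape is correct for stage 1 as planned, and inexact in stage 2 when negatives are kept and the share of positives is not about 67%. The departure from 0.050 one-sided is about 0.001 to 0.002 downward at 80% positives, and 0.0015 to 0.003 upward at 50% to 33% if the protocol minimum is missed.

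It would be wrong to conclude that the trial's actual error rate exceeds 0.10 two-sided. With stage 1 on plan and the futility rule followed, error stays well below nominal. What is not exact is the strong-control statement, which has to hold without that stop.

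The result rests on equal variance and information per participant in the two subgroups, independent endpoints, and the assumed rule for dropping negatives. If negatives were kept in every trial, the 33% figure would be 0.057.

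**What to change.** In SAP 7.4.1, replace the fixed 0.32 by a stage-specific shape λ_k = sqrt((1 − r_k)/(1 + r_k)). Define r_k as the square root of the proportion (or information share) of positives in stage k, or as the model-estimated correlation of T_k* and T_k^All. Name one of these in advance, and keep 0.32 as the planning value. State that the rule applies to stage 2 only when negatives are kept.

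The cost is one formula. The proportion of positives needs no outcome data, so the blinded statisticians, whom SAP 1.4 allows to amend the plan, can make the change. Sample size and conduct are unaffected.
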